### **6.2.3 Recruitment**

#### **a. Subject selection must be equitable; i.e., male/female, age range, racial and ethnic origin:**

Subjects will be selected and randomized into each group without discrimination by gender, race, or ethnicity. A predominantly female population is expected based on the historical patient population for bariatric surgery.

**b. Describe method of screening subjects and indicate when, where and how study subjects will be recruited, if applicable:**

For a bariatric patient to make it to their appointment to schedule their surgery, they will have already been screened as part of standard of care. This screening includes: ensuring BMI and comorbidities meet requirements to qualify for surgery, laboratory tests looking for an organic cause of obesity, psychiatric evaluation, upper endoscopy with gastric biopsies, ultrasound of the gallbladder if present, and several counseling sessions. Once all requirements have been met, they are seen in the bariatric clinic. Patients may choose which bariatric procedure they desire based on the information provided at the educational conferences without any coercion by staff to pick one procedure over another for research purposes. The educational conference is standardized and will not change as a result of implementation of this study. Staff may recommend the gastric bypass to certain patients based on excessive BMI or comorbidities, but the patient ultimately decides which surgery they desire based on all the information they are provided. When a patient had elected for a sleeve gastrectomy, he/she will be invited to speak with a research resident listed on the protocol, and a flyer pertaining to the project will be available for the patient to arrange a meeting to discuss the project. The research project representative will meet the patient, and details of the study will be discussed in person with patient. Pertinent topics of discussion will be that two different companies manufacture FDA-approved devices that are used for sleeve gastrectomies. Neither has been proven superior, and the aim of this study is to see if our institution has better results with one particular device in an effort to improve future patient care. The patient will be seen the day of surgery by a research representative, and he/she will be able to opt in or out at that time if they desire.

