### **6.3.4 Data Collection (*all study variables/instruments/questionnaires to be administered*):**

There will be two separate data logs maintained for the purposes of this study. The first log (master key) will contain all subject identifiers and PHI. Specifically, the master key will include:

- Patient identifier (to be linked to study log)
- Patient name
- Date of birth
- Surgeon
- Date of operation
- Family member prefix with last four digits of the social security number

The second log (data collection sheet) will include patient identifier to link to master key, but include no other PHI or direct identifiers. A data collection sheet that omits identifiable patient health information (only a pre-assigned identifier unique to the study) will be present in the operating room. This information will be transcribed to a data log on a secure computer. Specifically, the data collection sheet will include;

- Patient identifier (to link to master key)
- Gender
- Race
- Age
- Pre-operative height (needed to calculate ideal body weight)
- Pre-operative weight
- Intra-operative data points, to include time to load stapler, time to create sleeve, intra-operative bleeding or leak, and number of staple load misfires
- Weight recordings from follow-up appointments
- Annotations of any re-admissions or complications after surgery
- Follow-up weight (at follow up points)
- Weight loss (at follow up points)
- Need for hospital readmission or emergency room visits with annotation of the complication that caused the increased need for hospital care

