#### **6.4.2 Data analysis:**

For the continuous primary endpoints, the two-sample t-test for 2 means will be used to compare the 2 Devices at Surgery. For the continuous secondary endpoints, such as weight loss, the General Linear Mixed Model Analysis for repeated measures over time will be used to test for the Device effect, Time effect and the Device by Time Interaction. For the binary secondary endpoints (Yes/No), such as Staple line leak, Readmission or ER visits, further sleeve interventions, over time, the General Estimating Equations (GEE) analyses will be used to test for Device effect, Time effect and the Device by Time Interaction. For all tests, the level of significance is set at 0.05.

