#### **6.4.3 Sample Size Estimation:**

75 in each arm for a total of 150 patients. The preliminary power analysis indicated 64 in each arm to be sufficient, to be able to detect a medium effect size of 0.5 for the two-sided t-test, with  $\alpha = 0.05$  and 80% power, so 11 extra patients per arm have been added for attrition. The power analysis was based on the research hypothesis of a difference in the 2 devices, with this superiority study using time to create sleeve as the primary variable.

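### Sleeve creation time is compared without the surgeon stratum or recorded baseline covariates; a prespecified adjusted model is a cheap improvement, though the planned t-test is valid

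*Combined protocol and SAP*

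**What the plan says.** Section 6.4.2 specifies one method for continuous primary endpoints: "the two-sample t-test for 2 means will be used to compare the 2 Devices at Surgery". It adds "For all tests, the level of significance is set at 0.05". Section 6.4 names no covariate and no surgeon term.

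Section 6.4.3 sizes the trial for that unadjusted test, "with this superiority study using time to create sleeve as the primary variable". The effect is standardised, a "medium effect size of 0.5 for the two-sided t-test", with no standard deviation and no difference in seconds. It states "The preliminary power analysis indicated 64 in each arm to be sufficient", and the total is raised to 75 per arm for attrition.

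Two other parts of the protocol matter here:

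- **Allocation (Section 2.4).** There is one folder of cards per surgeon, three in all, each with 25 cards for each device. Surgeon is therefore a randomisation stratum.
- **Data (Section 6.3.4).** The data collection sheet carries gender, age, pre-operative height and pre-operative weight. BMI is not a listed field but can be computed. Surgeon is in the master key, which links to the sheet through the study identifier.

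**The concern.** The protocol itself suggests that surgeon and patient affect the timed interval. Section 2.4.1 says that the choice of loads after the first depends on both. Section 6.3.2 lets the sleeve be created by staff or by residents of differing seniority. Eligibility (Section 6.2.2) sets floors for BMI and no ceiling. Allocation balances device within surgeon, but nothing balances BMI, sex or age.

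A raw two-sample t-test leaves all such variation in the error term. For surgeon there is a further effect. Balancing the arms within surgeon removes between-surgeon variation from the true error of the device difference, but the t-test's standard error still includes it. The test is then conservative.

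Precision matters because the abstract (Section 2) says that cost may decide between the devices if neither proves superior. A true difference that is missed would feed that decision. A covariate list fixed in advance is uncontroversial; one added after the data are seen invites doubt about model selection.

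**Working it through.** **1. The plan's own figure.** Inputs from Sections 6.4.2 and 6.4.3: d = 0.5, two-sided alpha 0.05, power 80%, equal arms.

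- Normal approximation: n = 2(1.960 + 0.842)² / 0.5² = 62.8, so 63 per arm.
- Noncentral t at 64 per arm: noncentrality 0.5 × √(64/2) = 2.828 on 126 df, power 80.1%. The stated 64 reproduces.
- Attrition: 64 + 11 = 75 per arm, an allowance of 11/75 = 14.7%.
- If all 75 per arm are analysed: noncentrality 0.5 × √(75/2) = 3.062 on 148 df, power 86.0%.

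Sleeve time is measured at surgery, and Section 2.4 replaces patients who withdraw before surgery. The analysed number may therefore be near 75. Withdrawals after surgery with a request to remove data would lower it.

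**2. Adjusting for BMI, sex and age.** R² is the share of sleeve-time variance that the three explain. It is not in the documents, so 0 to 0.20 is an assumed range. With k = 3 covariates and N patients, chance imbalance inflates the variance of the adjusted difference by (N − 3)/(N − k − 3) on average. At N = 150 this is 147/144 = 1.021. Relative interval width is √[(1 − R²) × 147/144]. Power uses noncentrality 3.062 divided by that ratio, on 145 df.

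| Assumed R² | Relative width | Change in interval | Power, 75 per arm |
|---|---|---|---|
| 0 | 1.010 | 1.0% wider | 85.3% |
| 0.05 | 0.985 | 1.5% narrower | 87.0% |
| 0.10 | 0.959 | 4.1% narrower | 88.7% |
| 0.20 | 0.904 | 9.6% narrower | 92.0% |

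Simulation at 75 per arm agrees, with about 9.5% at the top end. Leaving out the imbalance term would give 1 − √(1 − R²), or 2.5% to 10.6%, which overstates the gain.

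Break-even is where (1 − R²)(N − 3)/(N − 6) = 1, that is R² = 3/(N − 3). This is 3/147 = 2.0% at N = 150 and 3/125 = 2.4% at N = 128.

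Simulation at 64 per arm (20,000 trials per value) gives adjusted power of 79.3%, 81.5%, 83.3% and 87.4% at R² of 0, 0.05, 0.10 and 0.20. The t-test gives about 80% to 81% throughout.

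**3. Surgeon.** Let S be the share of variance due to surgeon, again assumed. With exact balance within surgeon, the true variance of the device difference is (1 − S) times what the t-test assumes. At 64 per arm:

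- True two-sided alpha of the t-test: 2[1 − Φ(1.960/√(1 − S))].
- Its power: Φ[(2.828 − 1.960)/√(1 − S)].
- Power with surgeon in the model: noncentrality 2.828/√(1 − S) on 124 df.

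| Assumed S | True alpha, t-test | Power, t-test | Power, surgeon in model |
|---|---|---|---|
| 0.10 | 0.039 | 82% | 84% |
| 0.20 | 0.028 | 83% | 88% |
| 0.30 | 0.019 | 85% | 92% |

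Exact balance requires each folder to be used up. The tables in steps 2 and 3 are separate calculations, so their gains should not simply be added.

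**The case against.** The strongest reply is that nothing here is wrong. A two-sample t-test is valid in a randomised comparison, the sample size was computed for that test, and the figure reproduces. This stands in full. A reader might infer that the analysis is invalid or the trial undersized; the documents support neither. Ignoring a balanced stratum makes the test conservative, not liberal.

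The second reply is that the benefit from BMI, sex and age is unproven. A reader might infer that their precision is free because the data are already collected. The documents do not support that. They give no standard deviation for sleeve time and nothing linking these variables to it, and they weaken the mechanism in three ways:

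- The interval starts at the first firing. Section 2.4.1 places access, liver retraction and the greater-curvature dissection before that, so much of the work that body size could slow is not timed.
- Section 6.2.3 expects mostly women, which limits what sex can explain.
- The same section says "Staff may recommend the gastric bypass to certain patients based on excessive BMI or comorbidities". That may thin the upper BMI range, although the patient makes the final choice.

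These points make a value near the lower end of the assumed range credible. They do not remove the case for prespecification, because stomach size and number of firings fall within the timed interval and the downside is small. They also leave surgeon untouched. It is the covariate best supported by the documents, and a model with BMI, sex and age but no surgeon would be incomplete.

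**Conclusion.** The point holds as a cheap improvement. The planned test is sound but sets aside the allocation stratum and baseline data already recorded.

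If BMI, sex and age together explain an assumed 5% to 20% of variance, the interval at 75 per arm is about 1.5% to 9.5% narrower, and power at d = 0.5 rises from about 86% to about 87% to 92%. If they explain less than about 2%, there is no gain, with a possible loss of about 1% in width or one point of power. These figures assume that all 75 per arm are analysed and that covariate effects are linear. The surgeon figures rest on a separate assumed share. Only the direction, a conservative test if surgeons differ, follows from the design.

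**What to change.** In Section 6.4.2, before any outcome data are seen, replace the t-test as the main analysis of sleeve creation time with a linear model. It should contain device, surgeon (three levels, linked from the master key), pre-operative BMI as a continuous variable computed from recorded height and weight, sex, and age. Report the adjusted mean difference between devices with its 95% confidence interval, and give the unadjusted t-test as a check.

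The sample size in 6.4.3 can stay, since it is correct for the unadjusted test and any gain is unknown in advance. The cost is a sentence or two in 6.4.2, the link from the master key, and five model degrees of freedom (two for surgeon, three for the covariates). No new data are needed.

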comorbidities (hypertension, obstructive sleep apnea, pseudotumor cerebri, hyperlipidemia, diabetes, etc). All patients undergo psychiatric screening, laboratory assessment to rule out other cause of obesity, such as hypothyroidism, esophagogastroduodenoscopy, ultrasound of their gallbladder, and multiple counseling sessions prior to scheduling surgery. Patients may choose which bariatric procedure they prefer between sleeve gastrectomy, roux-en-y gastric bypass, and gastric band placement. Once scheduled for surgery, they will present to the hospital 6th floor. They will be given one dose of 5000 units subcutaneous heparin. Preoperative antibiotics of cefazolin or clindamycin will be administered within 30 minutes of surgery start time. Patients will be placed on the operating table in the supine position with a footboard in place. Sequential compression devices will be placed on the lower extremities. General endotracheal anesthesia will be induced. The abdomen will be prepped and draped in the usual sterile fashion. A time out will be completed, verifying the correct patient, procedure, site, positioning, and special equipment prior to starting the surgery. A fenestrated bougie will be placed through the patient's mouth, into the stomach. Pneumoperitoneum will be obtained, and a trocar with a laparoscope will be inserted. The abdominal contents will be inspected for evidence of injury. Three additional trocars will be placed under direct visualization and a Nathanson retractor will be used to retract the liver. Negative pressure will be applied to the fenestrated bougie after proper positioning laparoscopically. The stomach will be inspected, and a site 4-6 cm proximal to the pylorus will be identified. A defect will be made in the greater omentum at this site close to the greater curvature of the stomach using a harmonic scalpel. Dissection will be carried along the greater curvature of the stomach to the gastroesophageal junction, taking care not to injure the spleen. Starting with a black load with and absorbable polymer membrane reinforcement on either the Covidien iDrive with reinforced Tristaple technology or the Ethicon Echilon powered stapling device with Gore Seamguard reinforcement. Typically at our institution, the Ethicon Echilon device is used more frequently simply due to availability, but all bariatric surgeons are trained on both devices. Subsequent stapler loads will be surgeon and patient-dependent. Typically Ethicon black loads will be used until the fundus of the stomach, at which point a blue load without reinforcement is used. For Covidien, the black load is typically exchanged for a purple load near the fundus. Once the sleeve is complete, the stomach will be submerged in saline, and the remnant stomach will be insufflated, looking for any evidence of air leak, which would be repaired prior to conclusion of the case. The staple line will be inspected for bleeding. The gastric remnant will be removed though a port, and the abdomen will be desufflated. Incisions will be closed with 4-0 monocryl and covered in Dermabond. Patients are kept NPO and monitored overnight with intravenous fluids. They are started on water sips the next morning and are advanced to a bariatric liquid diet if they tolerated water sips. If they have adequate pain and nausea control and are taking in adequate fluid, they are discharged home on post-operative day one. They will follow-up at week 3, week 6, month 3, month 6, and annually.

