**6.3.2 Study Methodology/Procedures:**

Patients who express an interest in bariatric surgery will attend a bariatric seminar and initiate the process of scheduling bariatric surgery per department protocol. Once qualified for surgery, the patients will present to bariatric clinic, which takes place in the general surgery clinic on Tuesdays, and have a one-on-one discussion about their desired surgery with a staff physician. If the patient desires a sleeve gastrectomy, the study will be discussed. Consent will be obtained, and the patient will be randomized into the Covidien or Ethicon group. The subject will proceed with surgery per department protocol. In the operating room, a data collection sheet will be available in the operating room to make note of time for creation of sleeve from first firing to completion, total number of staple loads fired, number of misfires, character of any bleeding at the staple line and which interventions were required to control it, and time it takes for the surgical technologist to reload the stapler. At William Beaumont surgical technologists are trained on loading each linear cutting stapler by the Covidien and Ethicon representatives. We will still ensure at the start of the case they are familiar with loading the provided device. No additional training for device will be mandated, as surgical technologist turnover would make this difficult to provide equal training, and it would detract from internal and external validity, since we do not normally provide extra training. Typically the sleeve is created by staff or higher level residents (PGY-2 and above). However, all residents are trained on the devices and are therefore capable of creating the sleeve with close staff supervision, as is standard for our institution. For the purpose of this study, we intend on maintaining this practice since all level residents may be assisting and performing this surgery throughout their residency and deviation would lead to questionable internal validity. After surgery, patients will be admitted to the hospital, and care will follow the department's bariatric protocol. Once discharged, they will follow-up at 3 weeks, 6 weeks, 3 months, 6

months, and then annually. Subjects will be followed for 1 year after surgery. During that time, weight loss, presence of staple line leaks, any readmissions, and any other interventions will be monitored.

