### 6.3.7 Has any other Scientific Review Committee/Organization reviewed this project for scientific merit? Yes [ ] No [x]. If yes, name the organization, year, and merit/score:

#### 6.4 Statistical Consideration.

##### 6.4.1 Statistical hypothesis, primary endpoints (i.e., primary outcome variables), and secondary endpoints, if any:

Research Hypothesis: As a superiority study, the research hypothesis is Ethicon linear cutting staplers with staple line reinforcement will have different outcomes when performing laparoscopic sleeve gastrectomy when compared to Covidien staplers with staple line reinforcement.

Primary objectives: Determine if using different brand staplers affects:

1. Time of creation of sleeve from first firing to completion
2. The percent of firings with technical difficulties
3. The time for tech to load each staple cartridge (aware of Hawthorne effect. Since both arms will be subject to Hawthorne effect, the only variable should be the stapler)

Secondary objectives: Determine if using different brand staplers affects:

1. Any bleeding after creation of the sleeve (annotating whether single or multiple interventions are required)
2. Weight loss
3. Leak rates

4. Hospital readmissions or emergency room visits (For complications including but not limited to dehydration, hemorrhage, leak, internal hernia, and pain; will annotate what complication warranted readmission)
5. Further sleeve interventions

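### Section 6.4.2 tests readmission/ER visits and further sleeve interventions only by a GEE with Device, Time and Device-by-Time, and names no comparison of patients with any event within 1 year

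*Combined protocol and SAP*

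**What the plan says.** Section 6.4.1 lists among its secondary objectives whether stapler brand affects "Hospital readmissions or emergency room visits" and further sleeve interventions. It gives no time point and does not say whether patients or events are counted. Section 6.3.2 sets the horizon: "Subjects will be followed for 1 year after surgery", with clinic visits at 3 and 6 weeks, 3 and 6 months, and then annually.

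Section 6.4.2 gives the only analysis, for yes/no endpoints: "Readmission or ER visits, further sleeve interventions, over time, the General Estimating Equations (GEE) analyses will be used to test for Device effect". The same sentence puts a Time term and a Device-by-Time term under test as well. The section closes with one rule on error: "For all tests, the level of significance is set at 0.05". It does not state:

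- whether the outcome at each time is a new event since the last visit or status to date;
- which time levels are used;
- how Device is contrasted once the interaction is in the model;
- whether the interaction is removed if it is not significant;
- what is done when a time level has no events.

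Section 6.4.3 sizes the trial on sleeve creation time alone, "to be able to detect a medium effect size of 0.5 for the two-sided t-test". No binary endpoint has a power statement.

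**The concern.** A readmission, ER visit or re-intervention happens at some point in the year. It is not a state re-measured at each visit, so the natural question is how many patients in each arm had one within the year. The planned model divides the year into pieces and tests three terms. Depending on choices the plan leaves open, its Device term may describe only one piece, and sparse pieces may leave the model without an estimate.

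This matters because of the decision rule in the abstract (section 2). The device with better clinical outcomes is to be preferred whatever it costs, and cost decides only if neither is superior. Readmission for a complication and further surgery are among the outcomes listed there. A device answer that changes with the software's reference level is a poor basis for that rule.

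**Working it through.** **Step 1. The plan's own figure.** For d = 0.5, two-sided 0.05 and 80% power, the normal approximation is n = 2 × ((1.960 + 0.842)/0.5)² = 62.8, so 63 per arm. The exact t-test needs 64 (power 80.1%). Then 64 + 11 = 75 per arm. Section 6.4.3 reproduces, but it concerns sleeve time only.

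**Step 2. What the Device term estimates.** Take an illustrative data set of 75 per arm with one event per patient, and five windows ending at 3 weeks, 6 weeks, 3 months, 6 months and 1 year. Events are 6, 3, 3, 2, 1 (15 patients) against 14, 5, 4, 3, 4 (30 patients).

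- First window as reference: log OR = ln(14/61) − ln(6/69) = 0.971; SE = √(1/14 + 1/61 + 1/6 + 1/69) = 0.519; p = 0.061.
- Last window as reference: log OR = ln(4/71) − ln(1/74) = 1.428; SE 1.130; p = 0.21.
- Sum-to-zero coding: 0.732, the plain average of the five window log ORs; p = 0.034.
- No interaction: 0.754; p = 0.010.
- Status to date, last visit as reference: 0.981, exactly the 1-year log OR; p = 0.008.
- Per-patient comparison, 20% vs 40%: z = 0.20/√(0.30 × 0.70 × 2/75) = 2.67; p = 0.0075.

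Fitted GEEs (independence working correlation, robust errors) gave these Device values. On the same data the verdict at 0.05 changes with a choice that section 6.4.2 does not make.

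**Step 3. Empty windows.** The documents give no readmission/ER or re-intervention rate and no event timing, so these are assumptions: 1-year risk 15% vs 35%, first events split 50/20/15/10/5% over the windows. The chance that a window has no event in an arm is (1 − risk × share)^75. For the last window this is (1 − 0.0075)^75 = 0.57 in the lower-risk arm and (1 − 0.0175)^75 = 0.27 in the other. Treating the ten arm-by-window cells as independent, the chance that none is empty is about 0.14. Simulation gives at least one empty cell in 86% of trials. At 3% vs 6% or 3% vs 10% it is over 99%. Even with events spread evenly, the 3% arm has all five windows filled with probability only (1 − 0.994^75)^5 = 0.363^5 = 0.006. An empty cell gives an infinite log OR for that window.

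**Step 4. Power of the per-patient test, 75 per arm, 15% vs 35%.** Power = Φ((0.20 − 1.96 × √(0.25 × 0.75 × 2/75)) / √((0.1275 + 0.2275)/75)) = Φ((0.20 − 0.1386)/0.0688) = Φ(0.89) = 81%. Simulation gives 82%.

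**Step 5. Power of the Device term, first window as reference, same risks.** Only the share of events in that window matters. A trial with no finite estimate counts as not significant.

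| Share of events in reference window | Power of Device term | Trials with an empty cell |
|---|---|---|
| 20% (even spread) | 6% | 43% |
| 50% | about 42% | 86% |
| 70% (rest 15/8/5/2%) | 62% | 99% |

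Check on the 50% row: window risks are 0.075 and 0.175, log OR 0.962, SE 0.533, so power is about Φ(1.80 − 1.96) = 44%.

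Dropping the interaction restores power to 81% to 83%. Averaging over windows, with 0.5 added to make estimates finite, gives 70% (even spread) or 48% (half in the first window).

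**Step 6. Low rates.** At 3% vs 6% the per-patient test has about 13% power (14% by formula). At 3% vs 10% it has 41% by formula.

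**The case against.** The strongest reply is that section 6.4.2 never says Device will be read from one reference-level coefficient. It lists three effects to test and leaves the coding to the analyst. Step 2 shows that status-to-date coding with the last visit as reference returns the 1-year effect exactly, and that a model without the interaction loses almost nothing. This stands. A reader might infer that the planned Device test is a one-window test, or that about half the power is lost. The text supports neither: both need interval outcomes, reference coding and a particular event timing. With 70% of events in the reference window the loss is about a quarter (1 − 62/82 = 24%).

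A reader might also infer that these endpoints are common enough to show a device difference. The documents do not say so. Their only figures are leak 2.8% and hemorrhage 3% (section 5.1) and complications of 1% to 5% (section 6.5.2). The endpoint in 6.4.1 is broader, covering visits for pain and dehydration, but no rate is given, and at low rates a per-patient test is weak too.

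A further argument, that readmission cannot occur at a day-1 time level because "they are discharged home on post-operative day one", has force only if day 1 is used as a level, and 6.4.2 does not say that it is.

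What the reply does not answer is that no 1-year per-patient comparison is named, that the interaction is explicitly part of the plan, and that with interval outcomes and separate time levels it will often be inestimable. Low rates make that worse.

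**Conclusion.** The point holds as a mismatch between question and method. These two endpoints have one planned analysis, it includes Device-by-Time, and no comparison of patients with any event within 1 year is named. Under interval outcomes and reference coding the Device term is a one-window effect that depends on the reference. With windows as separate levels, an empty cell is likely: about 86% of trials at 15% vs 35% with half of events in the first window, and nearly all at 3% vs 6% to 10%.

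The firm part is the missing 1-year comparison and the fragility of the interaction model. The power figures (82% against 42%, 62% or 6%) are illustrations on assumed rates and timing, not properties of the plan. The endpoints are secondary and unpowered, so no stated power is broken. The change is still worth making because section 2 lets clinical outcomes override cost.

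**What to change.** In section 6.4.2, for readmission/ER visits and for further sleeve interventions separately:

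- Make the main analysis the proportion of patients with at least one event within 1 year of surgery, compared by risk difference with 95% CI and one two-sided test at 0.05, exact if events are sparse.
- Stratify by surgeon, because section 2.4 randomises from a separate card folder for each of three surgeons.
- Report event timing by window, and repeat events, descriptively. Do not rely on the Device-by-Time model for the device conclusion.
- State how patients lost before 1 year are handled, for example Kaplan-Meier 1-year risks by arm, or a sensitivity analysis of complete cases. Section 6.4.3 allows for 11 of 75 per arm (14.7%).

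The cost is a few sentences. Section 6.3.4 already collects readmissions, ER visits and complications, so no new data are needed. The downsides are that repeat events in one patient collapse to a single yes, that the formal test of whether the device effect changes over time is given up for these endpoints, and that the loss-to-follow-up rule needs some thought. The change will not rescue power if event rates are low, but it gives an interpretable estimate and interval.
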